
Potential risk of alterations in immune response potentially leading to increase in malignancies
	
 Non-clinical and clinical experience to date does not support a role for mepolizumab in the development of malignancies. No evidence of defective tumor surveillance in IL-5 or eosinophil-deficient mice. Mepolizumab is not believed to possess an inherent carcinogenic potential or increase the susceptibility to tumor formation secondary to significant immunosuppression, and there is no evidence to date that mepolizumab has produced immunosuppression in animals. Reports of malignancies in the overall 	
 Participants with current malignancy or malignancy that developed during Study 200622 will be excluded from the study. Participants who had localized carcinoma (i.e., basal or squamous cell) of the skin which was resected for cure will not be excluded. Daily monitoring of SAEs by GSK Medical Monitor; regular systematic review of AE/SAE data from this study by GSK study team and/or GSK safety review team

Potential Risk of Clinical Significance	Summary of Data/Rationale for Risk	Mitigation Strategy
	
mepolizumab program (including asthma, HES, other eosinophil-driven diseases & healthy participants) were similar across treatment groups and are those types common in the general population with a frequency rate of <1% at all individual doses and all doses of mepolizumab combined.
 
A review of a well-established cohort of patients with hyper eosinophilia including those with HES at the Mayo clinic showed that 5.1% developed hematologic malignancy over 13-year period; the median time the malignancy developed was 10 months after the onset of hypereosinophilia. T-cell derived malignancies were most commonly diagnosed [Jin, 2015].
 
Malignancies, including lymphoma, reported to date across the mepolizumab program (severe asthma and HES) are summarized in the IB; see also 'Special Warnings and Special Precautions for Use' section located in IB Section 6 titled 'Summary of Data and Guidance for the Investigator'.
	

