6.1. Inclusion Criteria

Participants are eligible to be included in the study only if all of the following criteria apply:

Study 200622 requirements

1. Age 12 years and older participants who were enrolled in Study 200622.
To be considered for Study 205203, Study 200622 participants must have completed 32-week assessments since randomization:
 - (i) Completion of the 32-week treatment period in Study 200622
OR
 - (ii) If the participant was withdrawn from study treatment prematurely during the 200622 study, but continued in the study per protocol (including HES flare-related assessments) until 32 weeks from randomization.

Sex

2. Male or female

Female participants:

A female participant who meets one of the following conditions:

- (i) Not a woman of childbearing potential (WOCBP) as defined in [Appendix 5](#)
OR
- (ii) A WOCBP who agrees to follow the contraceptive guidance in [Appendix 5](#) at least 30 days prior to the first dose of study treatment and until 16 weeks after the last dose of study treatment.

Positive benefit:risk ratio

3. The treating physician must confirm a positive benefit/risk ratio. The anticipated clinical benefit from mepolizumab must outweigh any potential safety or tolerability risk in Study 205203.

Informed consent

4. Capable of giving signed informed consent as described in [Appendix 3](#) which includes compliance with the requirements and restrictions listed in the informed consent form (ICF) and in this protocol.

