8. TREATMENT DISCONTINUATION CRITERIA

8.1. Discontinuation of Study Treatment

Participants who discontinue study treatment prematurely (for any reason) should, where possible, continue in the study per protocol (Refer to SoA) until 20 weeks after the first dose of mepolizumab in study 205203 (Visit 7), including the collection of biological

samples for laboratory assessments approximately 4 weeks and 12 weeks after the last dose of mepolizumab.

If a participant experiences an organ-threatening or a life-threatening event, the investigator should discuss continuation of mepolizumab with the GSK Medical Monitor.

Participants will be withdrawn from treatment with mepolizumab for any of the following reasons:

[figure not shown]
- **Pregnancy:** Any female subject who becomes pregnant.
- Meet the **liver chemistry stopping criteria** (Section 8.1.1)
- Meet **QTc stopping criteria** (Section 8.1.2).

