13.2.1. Treatment Phases for Adverse Events

Treatment State	Definition
Pre-Treatment	
 AE start date < Date of first dose of open-label mepolizumab or if AE onset date/time is available AE start date/time < Date/time of first dose of open-label mepolizumab
On-Treatment	
 Date of first dose of open-label mepolizumab ≤ AE start date ≤ Date of last dose of open-label mepolizumab + 28 days or if AE onset date/time is available Date/time of first dose of open-label mepolizumab ≤ AE start date/time ≤ Date/time of last dose of open-label mepolizumab + 28 days Any adverse event with missing start date will be assumed to be “On-Treatment”. Any adverse event with partial start date will be assumed to be “On-Treatment” unless there is evidence to the contrary (e.g. month/year of onset is present and is earlier than the month/year of the first dose of study treatment).
Post-Treatment	
 AE start date > Date of last dose of open-label mepolizumab + 28 days or if AE onset date/time is available AE start date/time > Date/time of last dose of open-label mepolizumab + 28 days

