2.21.	Safety	AE1	Summary of All On-Treatment Serious Adverse Events by System Organ Class and Preferred Term		SAC

CONFIDENTIAL

205203

No.	Population	IDSL / Example Shell	Title	Programming Notes	Deliverable
2.22.	Safety	AE1	Summary of All Post-Treatment Serious Adverse Events by System Organ Class and Preferred Term		SAC
2.23.	Safety	AE1	Summary of All Pre-Treatment Serious Adverse Events by System Organ Class and Preferred Term		SAC
2.24.	Safety	AE16	Summary of All Serious Adverse Events by System Organ Class and Preferred Term (Number of Subjects and Occurrences)		SAC
2.25.	Safety	AE1	Summary of All Drug-Related Serious Adverse Events by System Organ Class and Preferred Term		SAC
Adverse Events of Special Interest					
2.26.	Safety	AE1	Summary of On-Treatment Adverse Events Reported by the Investigator as Systemic Reactions Meeting the Criteria for Anaphylaxis		SAC
2.27.	Safety	SAFE_T2	Summary Profile of On-Treatment Adverse Events Reported by the Investigator as Systemic Reactions Meeting the Criteria for Anaphylaxis		SAC
2.28.	Safety	AE1	Summary of On-Treatment Adverse Events Reported by the Investigator as Systemic Reactions - Allergic (Type I Hypersensitivity) and Other Systemic		SAC
2.29.	Safety	SAFE_T2	Summary Profile of On-Treatment Adverse Events by the Investigator as Systemic Reactions - Allergic (Type I Hypersensitivity) and Other Systemic		SAC
2.30.	Safety	AE1	Summary of On-Treatment Adverse Events Reported by the Investigator as Systemic Reactions - Allergic (Type I Hypersensitivity)		SAC

CONFIDENTIAL

205203

No.	Population	IDSL / Example Shell	Title	Programming Notes	Deliverable
2.31.	Safety	SAFE_T2	Summary Profile of On-Treatment Adverse Events Reported by the Investigator as Systemic Reactions - Allergic (Type I Hypersensitivity)		SAC
2.32.	Safety	AE1	Summary of On-Treatment Adverse Events Reported by the Investigator as Systemic Reactions – Other Systemic		SAC
2.33.	Safety	SAFE_T2	Summary Profile of On-Treatment Adverse Events Reported by the Investigator as Systemic Reactions - Other Systemic		SAC
2.34.	Safety	AE1	Summary of On-Treatment Adverse Events Reported by the Investigator as Local Injection Site Reactions		SAC
2.35.	Safety	SAFE_T2	Summary Profile of On-Treatment Adverse Events Reported by the Investigator as Local Injection Site Reactions		SAC
2.36.	Safety	AE1	Summary of On-Treatment Adverse Events Categorised as Serious Cardiac, Vascular and Thromboembolic Events		SAC

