2.37.	Safety	SAFE_T2	Summary Profile of On-Treatment Adverse Events Categorised as Serious Cardiac, Vascular and Thromboembolic Events		SAC
2.38.	Safety	AE1	Summary of On-Treatment Adverse Events Categorised as Serious Ischemic Events		SAC
2.39.	Safety	SAFE_T2	Summary Profile of On-Treatment Adverse Events Categorised as Serious Ischemic Events		SAC
2.40.	Safety	AE1	Summary of On-Treatment Adverse Events Categorised as Malignancies		SAC
2.41.	Safety	SAFE_T2	Summary Profile of On-Treatment Adverse Events Categorised as Malignancies		SAC

No.	Population	IDSL / Example Shell	Title	Programming Notes	Deliverable
2.42.	Safety	AE1	Summary of On-Treatment Adverse Events Categorised as Potential Opportunistic Infections		SAC
2.43.	Safety	SAFE_T2	Summary Profile of On-Treatment Adverse Events Categorised as Potential Opportunistic Infections		SAC
Laboratory – Haematology					
2.44.	Safety	LB1	Summary of Haematology Changes from Baseline by Visit	Include baseline values	SAC
2.45.	Safety	LB3	Summary of Haematology Shifts from Baseline Relative to Normal Range by Visit	Include worst case post-baseline. If there are unscheduled assessments add footnote: "Note: Worst case post baseline Includes scheduled and unscheduled assessments."	SAC
2.46.	Safety	LB3	Summary of Haematology Shifts from Baseline Relative to PCI Criteria by Visit	Include worst case post-baseline. If there are unscheduled assessments add footnote: "Note: Worst case post baseline Includes scheduled and unscheduled assessments."	SAC
Laboratory – Clinical Chemistry					
2.47.	Safety	LB1	Summary of Clinical Chemistry Changes from Baseline by Visit	Include baseline values	SAC
2.48.	Safety	LB3	Summary of Clinical Chemistry Shifts from Baseline Relative to Normal Range by Visit	Include worst case post-baseline. If there are unscheduled assessments add footnote: "Note: Worst case post baseline Includes scheduled and unscheduled assessments."	SAC

No.	Population	IDSL / Example Shell	Title	Programming Notes	Deliverable
2.49.	Safety	LB3	Summary of Clinical Chemistry Shifts from Baseline Relative to PCI Criteria by Visit	Include worst case post-baseline. If there are unscheduled assessments add footnote: "Note: Worst case post baseline Includes scheduled and unscheduled assessments."	SAC
Laboratory – Urinalysis					
2.50.	Safety	UR1	Summary of Worst Case Urinalysis Results Post-Baseline Relative to Baseline		SAC
Laboratory: Hepatobiliary (Liver)					

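### The summary tables for malignancy, serious CVT, serious ischaemic and opportunistic-infection events stop 28 days after the last dose, so no table gives a post-treatment count by category although the protocol keeps collecting adverse events

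*SAP*

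**What the plan says.** The SAP's list of safety tables (13.8.5) gives each of the four categories a summary table and a profile table, numbered 2.36 to 2.43. The four summary titles are:

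- Table 2.36: "Summary of On-Treatment Adverse Events Categorised as Serious Cardiac, Vascular and Thromboembolic Events"
- Table 2.38: "Summary of On-Treatment Adverse Events Categorised as Serious Ischemic Events"
- Table 2.40: "Summary of On-Treatment Adverse Events Categorised as Malignancies"
- Table 2.42: "Summary of On-Treatment Adverse Events Categorised as Potential Opportunistic Infections"

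The matching profile tables (2.37, 2.39, 2.41, 2.43) carry the same limit. SAP 13.2.1 assigns an event to a phase by its start date. The post-treatment phase is "AE start date > Date of last dose of open-label mepolizumab + 28 days", so the on-treatment phase runs from the first open-label dose to day 28 after the last one.

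SAP 7.2 describes the AESI output without any phase limit. It promises the number and percentage of participants for each type, and a profile covering matters such as time to onset, intensity, outcome and action taken.

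The protocol observes for longer. Section 8.1 states: "Participants who discontinue study treatment prematurely (for any reason) should, where possible, continue in the study per protocol". That follow-up runs to 20 weeks after the first dose, with samples about 4 and 12 weeks after the last dose. Participants who do not move to expanded access attend Visit 7, 12 weeks after the last dose (5.1). The Schedule of Activities marks AE and SAE review at that visit.

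**The concern.** The study exists to describe long-term safety, and adverse events are a primary endpoint. The protocol pays for follow-up after treatment ends, but the four category summaries do not use it. SAP 7.2 and the display list therefore differ in scope, and no reason is given.

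The treatment of the post-treatment period is also uneven. General adverse events have a post-treatment table (2.2), as do SAEs (2.22), and flares are analysed with follow-up after treatment discontinuation retained (SAP 9.1.1.3). The AESI categories have no post-treatment or all-phase summary.

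These are rare events, likely to number very few in a study of this size. One event that starts, say, five weeks after the last dose in a participant still being followed would leave the category table at 0.

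**Working it through.** The documents state no event rate, number of early stoppers or number of Visit 7 attendees, so there is no plan figure to reproduce. What can be calculated is the follow-up that falls outside the tables.

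**Inputs**

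- Doses every 4 weeks, five in all: days 0, 28, 56, 84 and 112 (Protocol 5.1, 7.3).
- On-treatment end = last dose + 28 days (SAP 13.2.1).
- End of follow-up without expanded access = the later of day 140 (Week 20) and last dose + 84 days (Protocol 8.1 and Schedule of Activities).
- Timing check: Week 16 + 12 weeks = Week 28, which agrees with the protocol's timing for Visit 7.

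**Formula:** days outside = end of follow-up − on-treatment end; share = days outside / end of follow-up.

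| Participant | Last dose (day) | On-treatment ends | Follow-up ends | Days outside | Share |
|---|---|---|---|---|---|
| 5 doses, expanded access at Week 20 | 112 | 140 | 140 | 0 | 0% |
| 5 doses, Visit 7 | 112 | 140 | 196 | 56 | 28.6% |
| Stops after 4 | 84 | 112 | 168 | 56 | 33.3% |
| Stops after 3 | 56 | 84 | 140 | 56 | 40.0% |
| Stops after 2 | 28 | 56 | 140 | 84 | 60.0% |
| Stops after 1 | 0 | 28 | 140 | 112 | 80.0% |

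**Sensitivity**

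- With the ±1 week window, Visit 7 leaves 84 − 7 − 28 = 49 to 84 + 7 − 28 = 63 days outside.
- A Visit 6 that is 7 days late (day 147) leaves 147 − 140 = 7 days outside for a completer entering expanded access.
- If a four-dose stopper is followed only to Week 20, the figure is 140 − 112 = 28 of 140 days (20%).
- Counting both end days for the one-dose stopper gives 112/141 = 79%.

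Protocol 8.1 attaches the label Visit 7 to the Week 20 time point, whereas 5.1 and the Schedule of Activities put Week 20 at Visit 6. These passages need to be reconciled.

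**Where a later event would appear**

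- Table 2.2 (post-treatment AEs), by system organ class and preferred term.
- If serious, Table 2.22 (post-treatment SAEs), and Tables 2.20 and 2.24, whose titles carry no phase limit.
- Listings 22-25, by AESI category, with the phase shown.

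Only the listings group later events by category. The categories come from a project-level preferred-term list (SAP 7.2), so a reader cannot rebuild a category n (%) from preferred-term lines. SAP 13.3.2 keeps subject-level listings out of the main body of the report. The malignancy and opportunistic-infection tables are not confined to serious events, so a non-serious late case would not reach the SAE tables either.

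**Weight of one event.** The parent study's ceiling is 120 randomised participants (Protocol 5.2). Taking that as an upper bound here, one event is at least 1/120 = 0.8 percentage points in the total column, and more within each previous-treatment column.

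**The case against.** The strongest reply is that the report already contains these events. Serious CVT and serious ischaemic events are serious by definition and so reach Table 2.22. Protocol Appendix 4 names invasive or malignant cancers among events that should usually be considered serious. A note to the listings promises subject profiles for deaths and cardiovascular events. With very few events expected, a listing by category shows the count at once. The 28-day window is also coherent: it equals the dosing interval and is used for time on treatment (SAP 13.2), exposure (13.4.3) and blood eosinophils (11.1.4). Pooling later events would mix participants with unequal follow-up. All of this stands. It rules out any claim of data loss and is a reason to keep the on-treatment columns. It does not supply the post-treatment n (%) and profile by category that SAP 7.2 appears to promise.

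A reader might infer four stronger points that the documents do not support.

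- **The window is too short for the malignancy latency the protocol cites.** Protocol 3.3.1 says "the median time the malignancy developed was 10 months after the onset of hypereosinophilia". That interval starts at disease onset in a patient cohort, not at dosing, so it sets no post-dose window.
- **The window conflicts with a 16-week precaution period.** The words "until 16 weeks after the last dose of study treatment" belong to the contraception requirement, which does not define adverse event follow-up.
- **Stopping treatment because of an AESI removes it from its table.** Phase depends on the recorded start date. An event that begins before the stop, or within 28 days of the last dose, stays in. Missing start dates, and partial ones without contrary evidence, default to on-treatment. Only an event whose recorded start falls beyond day 28 drops out. That could happen if a diagnosis is dated after work-up, but the documents do not say how such events are dated.
- **The primary endpoint suffers informative censoring.** That endpoint covers all adverse events and anti-drug antibody. Tables 2.1 and 2.2 together cover both phases for adverse events. The AESI tables are descriptive subsets with no time-to-event analysis, and no hypothesis is tested.

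**Conclusion.** The point holds as a reporting gap of minor severity. Tables 2.36-2.43 omit between 29% and 80% of nominal follow-up for participants who attend Visit 7 or stop early with follow-up as scheduled, and essentially none for completers who enter expanded access at Week 20. No listed summary table supplies a post-treatment n (%) or profile by category, so one of these tables could read 0 when a followed participant had an event starting beyond day 28.

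The shares assume nominal visit timing and follow-up to the later of Week 20 and 12 weeks after the last dose. The practical effect depends on how many participants stop early or attend Visit 7, which is unknown. The Adverse Event Overview (Table 2.16) has no phase limit in its title and might carry AESI rows. Its shell is not in the documents, so this cannot be confirmed.

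**What to change.** Keep the on-treatment columns in Tables 2.36-2.43. Beside them, add n (%) for the post-treatment phase and for all events from the first open-label dose onward, and show days since last dose in the four profile tables. State in SAP 7.2 which phases each AESI display covers. The systemic-reaction and injection-site tables (2.26-2.35) can stay as they are.

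The cost is small: eight table titles and specifications change. The phase flags and AESI categories already exist for Listings 22-25, and no new data are needed. The downside is that the all-post-first-dose incidence may look slightly less favourable and rests on follow-up that differs by roll-over status. Showing the two phases separately makes that visible.

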13.8.6. Safety Figures

Safety: Figures					
No.	Population	IDSL / Example Shell	Title	Programming Notes	Deliverable
Laboratory					
2.1.	Safety	LIVER14	Scatter Plot of Maximum vs Baseline for ALT	If there are unscheduled assessments add footnote: "Note: Maximum Value includes scheduled and unscheduled assessments."	SAC

Safety: Figures					
No.	Population	IDSL / Example Shell	Title	Programming Notes	Deliverable
2.2.	Safety	LIVER9	Scatter Plot of Maximum Total Bilirubin vs Maximum ALT	If there are unscheduled assessments add footnote: "Note: Maximum Value includes scheduled and unscheduled assessments."	SAC

13.8.7. Efficacy Tables

Efficacy: Tables					
No.	Population	IDSL / Example Shell	Title	Programming Notes	Deliverable
HES Flare					
3.1.	Safety	EFF_T1	Overview of HES Flares		SAC
3.2.	Safety	EFF_T2	Summary of Frequency of All HES Flares		SAC
3.3.	Safety	EFF_T3	Summary of Rate of HES Flares by Study (Study 200622 and Study 205203) (Treatment Policy Estimand)		SAC
3.4.	Safety	EFF_T4	Summary of Mean Prednisone Equivalent Daily OCS Dose Over Time		SAC
3.5.	Safety	EFF_T5	Summary of Change from Week 0-4 in Mean Prednisone Equivalent Daily OCS Dose Over Time		SAC
3.6.	Safety	EFF_T5	Summary of Change from Week 0-4 in Mean Prednisone Equivalent Daily OCS Dose Over Time – Subjects with Mean Week 0-4 OCS Dose >0mg		SAC
3.7.	Safety	EFF_T6	Proportion of Subjects Who Achieve a Mean Daily OCS Dose \leq 7.5mg Over Time		SAC
3.8.	Safety	EFF_T7	Proportion of Subjects Who Achieve a Mean Daily OCS Dose Reduction of \geq 50% Over Time – Subjects with Mean Week 0-4 OCS Dose >0mg		SAC

13.8.8. Efficacy Figures

Efficacy: Figures						
No.	Population	IDSL / Example Shell	Title	Programming Notes	Deliverable	
HES Flare						
3.1.	Safety	EFF_F1	Cumulative Number of HES Flares		SAC	

13.8.9. Pharmacokinetic Tables

Pharmacokinetic: Tables					
No.	Population	IDSL / Example Shell	Title	Programming Notes	Deliverable [Priority]
4.1.	Safety	PK01	Summary of Plasma Mepolizumab Concentration-Time Data (by previous treatment group from study 200622 and by immunogenicity status)		SAC

13.8.10. Pharmacodynamic Tables

Pharmacodynamic: Tables					
No.	Population	IDSL / Example Shell	Title	Programming Notes	Deliverable
Blood Eosinophils					
6.1.	PD	PD_T1	Summary of On-Treatment Blood Eosinophil Count	Include absolute blood eosinophils at Screening, Baseline and Week 4 through Week 20. Number of decimal places as follows: geometric mean (2), SD logs (3), median (2), min (2), max (2).	SAC
6.2.	PD	PD_T2	Summary of On-Treatment Ratio to Baseline Blood Eosinophils	Include Week 4 through Week 20.	SAC

13.8.11. Pharmacodynamic Figures

Pharmacodynamic: Figures					
No.	Population	IDSL / Example Shell	Title	Programming Notes	Deliverable
Blood Eosinophils					
6.1.	PD	EFF_F4	On-Treatment Absolute Blood Eosinophils	No reference line. Include screening and baseline unadjusted geometric mean values.	SAC
6.2.	PD	EFF_F4	On-Treatment Ratio to Baseline Blood Eosinophils	Reference line at 1.	SAC

13.8.12. ICH Listings

ICH: Listings					
No.	Population	IDSL / Example Shell	Title	Programming Notes	Deliverable
Subject Disposition					
1.	Screened	ES7	Listing of Reasons for Screen Failure		SAC
2.	Safety	ES2	Listing of Reasons for Study Withdrawal		SAC
3.	Safety	SD2	Listing of Reasons for Study Treatment Discontinuation		SAC
Protocol Deviations					
4.	Safety	DV2	Listing of Important Protocol Deviations		SAC
5.	Safety	IE3	Listing of Subjects with Inclusion/Exclusion Criteria Deviations		SAC
Populations Analysed					
6.	Safety	SP3	Listing of Subjects Excluded from Any Population	Include Safety, PD	SAC

ICH: Listings					
No.	Population	IDSL / Example Shell	Title	Programming Notes	Deliverable
Demographic and Baseline Characteristics					
7.	Safety	DM2	Listing of Demographic Characteristics		SAC
8.	Safety	DM9	Listing of Race		SAC
Prior and Concomitant Medications					
9.	Safety	CP_CM3	Listing of Concomitant Medications	Flag baseline HES therapy on listing.	SAC
Exposure and Treatment Compliance					
10.	Safety	EX3	Listing of Exposure Data	Exposure to Mepolizumab only	SAC
Efficacy					
11.	Safety	EFF_L1	Listing of Investigator Reported HES Flare		SAC
Adverse Events					
12.	Safety	AE8	Listing of All Adverse Events	Add phase: Pre-treatment, on-treatment, post-treatment. Include treatment in by-line.	SAC
Serious and Other Significant Adverse Events^[1]					
13.	Safety	AE8	Listing of Fatal Serious Adverse Events	Add phase: Pre-treatment, on-treatment, post-treatment. Include treatment in by-line.	SAC
14.	Safety	AE8	Listing of Non-Fatal Serious Adverse Events	Add phase: Pre-treatment, on-treatment, post-treatment. Include treatment in by-line.	SAC
15.	Safety	AE14	Listing of Reasons for Considering as a Serious Adverse Event	Add phase: Pre-treatment, on-treatment, post-treatment. Include treatment in by-line.	SAC

ICH: Listings					
No.	Population	IDSL / Example Shell	Title	Programming Notes	Deliverable
16.	Safety	AE8	Listing of Adverse Events Leading to Withdrawal from Study / Permanent Discontinuation of Study Treatment	Add phase: Pre-treatment, on-treatment, post-treatment. Include treatment in by-line.	SAC
17.	Safety	AE8	Listing of Adverse Events Reported on the Day of Dosing	Add phase: Pre-treatment, on-treatment, post-treatment. Include treatment in by-line.	SAC
18.	Safety	AE8	Listing of Adverse Events Reported by the Investigator as Systemic Reactions Meeting the Criteria for Anaphylaxis	Add phase: Pre-treatment, on-treatment, post-treatment. Add injection reaction symptoms and number of doses prior to event. Include treatment in by-line.	SAC
19.	Safety	AE8	Listing of Adverse Events Reported by the Investigator as Systemic Reactions - Allergic (Type I Hypersensitivity)	Add phase: Pre-treatment, on-treatment, post-treatment. Add injection reaction symptoms and number of doses prior to event. Include treatment in by-line.	SAC
20.	Safety	AE8	Listing of Adverse Events Reported by the Investigator as Systemic Reactions – Other Systemic	Add phase: Pre-treatment, on-treatment, post-treatment. Add injection reaction symptoms and number of doses prior to event. Include treatment in by-line.	SAC

ICH: Listings					
No.	Population	IDSL / Example Shell	Title	Programming Notes	Deliverable
21.	Safety	AE8	Listing of Adverse Events Reported by the Investigator as Local Injection Site Reactions	Add phase: Pre-treatment, on-treatment, post-treatment. Add injection reaction symptoms and number of doses prior to event. Include treatment in by-line.	SAC
22.	Safety	AE8	Listing of Adverse Events Categorised as Serious Cardiac, Vascular and Thromboembolic Events	Add phase: Pre-treatment, on-treatment, post-treatment. Include treatment in by-line.	SAC
23.	Safety	AE8	Listing of Adverse Events Categorised as Serious Ischemic Events	Add phase: Pre-treatment, on-treatment, post-treatment. Include treatment in by-line.	SAC
24.	Safety	AE8	Listing of Adverse Events Categorised as Malignancies	Add phase: Pre-treatment, on-treatment, post-treatment. Include treatment in by-line.	SAC
25.	Safety	AE8	Listing of Adverse Events Categorised as Potential Opportunistic Infections	Add phase: Pre-treatment, on-treatment, post-treatment. Include treatment in by-line.	SAC
Hepatobiliary (Liver)					
26.	Safety	MH2	Listing of Medical Conditions for Subjects with Liver Stopping Events	Programming note: Include all subjects meeting protocol defined liver stopping criteria even if liver pages were not completed by the site.	SAC
All Laboratory					
27.	Safety	LB5	Listing of Haematology Data for Subjects with Any Value of Potential Clinical Importance		SAC

ICH: Listings					
No.	Population	IDSL / Example Shell	Title	Programming Notes	Deliverable
28.	Safety	LB5	Listing of Clinical Chemistry Data for Subjects with Any Value of Potential Clinical Importance		SAC
29.	Safety	LB14	Listing of Laboratory Data with Character Results		SAC
30.	Safety	UR2A	Listing of Urinalysis Data for Subjects with Any Value of Potential Clinical Importance		SAC
ECG					
31.	Safety	EG3	Listing of All ECG Values for Subjects Meeting Protocol Defined QTc Stopping Criteria		SAC

ICH: Listings					
No.	Population	IDSL / Example Shell	Title	Programming Notes	Deliverable
Immunogenicity					
32.	Safety	SAFE_L1	Listing of Immunogenicity Data for Subjects with at Least One Positive Screening Binding Assay Result		SAC
Pharmacokinetic					
33.	Safety		Listing of Plasma Concentration		SAC
Pharmacodynamic					
34.	Safety	PD_L1	Listing of Blood Eosinophils (unit)		SAC

[1] For deaths and any cardiovascular events, subject profiles will be produced as per GSK IDSL standard template.

